	
endpoints in CDx+ subjects will be summarized and compared between PRA023 and placebo groups in FAS for CDx+, while the treatment difference will be estimated with 95% CI. Additional efficacy analysis will be detailed in SAP.
 
Interim Efficacy Analysis: An interim analysis will be carried out when approximately 80% of subjects (approximately 96 subjects) in Cohort 1 have reached Week 12 or early terminated from the study. The DMC will review the unblinded efficacy and safety data and recommend whether to continue enrollment into Cohort 2. Decision rules to continue Cohort 2 are to be determined according to the futility bounds of group sequential design of a sample size of 40 per arm with one interim analysis at the information fraction of 45%. Because the exact bounds will be calculated using the actual number of subjects with CDx+ included in the interim analysis, the final decision rules, along with sensitivity analysis, will be specified in the DMC SAP, prior to the interim analysis.
 
Adverse Events: AEs will be coded using the most current version of Medical Dictionary for Regulatory Activities (MedDRA®). A by-subject AE data listing, including verbatim term, preferred term (PT), system organ class (SOC), treatment, severity, seriousness criteria, relationship to drug, and action taken, will be provided. The number of subjects experiencing treatment-emergent adverse events (TEAEs) and number of TEAEs will be summarized by treatment using frequency counts for Safety analysis set. Medical History, chest x-ray, electrocardiogram (ECG), and physical examination will be listed by subject. Changes in ECGs and physical examinations will be described in the text of the final report.
 
Concomitant Medications: Concomitant medications will be coded using the most current World Health Organization (WHO) drug dictionary and listed by treatment.
 
Pharmacokinetics: Summary statistics of PRA023 concentrations and anti-drug antibody (ADA) by visit and by CDx+ and CDx-.

--	--

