### 6.3.4 Electrocardiogram (ECG)

A standard 12-lead ECG for all subjects will be performed at Screening and at the subsequent visits specified in the schedule of study procedures (Section 6.1.1). The original ECGs with interval printouts and rhythm strip run at 25 mm/sec must be provided as source documentation.

Automatically calculated QT and QTc intervals will be reviewed and checked for gross inaccuracies by the Investigator or designated ECG reviewer. If the automatically calculated QT or QTc intervals are greater than 480 msec, or if either has increased by 50 msec or more over the baseline value, it will be manually over-read by the Investigator or designated ECG reviewer. The ECG parameters that will be assessed include heart rate, PR interval, QRS interval, and QT interval. If QT or QTc interval prolongation exceeding these limits is verified during treatment, the subject's medical background should be examined closely for risk factors that may have contributed to the event, including genotyping for hereditary long QT syndromes, if appropriate.

Any sign of arrhythmia should be noted. During treatment, any indication of QT prolongation or Torsade de Pointes, a polymorphic ventricular tachyarrhythmia that appears on the ECG as continuous twisting of the vector of the QRS complex around the isoelectric baseline, must be recorded as an adverse event and reported to the Medical Monitor.

The decision to continue the treatment of any subject with prolonged QT or QTc interval must be discussed and agreed upon by the Investigator and the Medical Monitor. All such subjects, including subjects with cardiac arrhythmias, should be monitored closely. If appropriate, ECG monitoring should be performed until the QT and QTc interval and waveform morphology have returned to normal. If the prolongation or abnormal rhythm persists, the Medical Monitor must be contacted.

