### 8.3 Evaluation of Safety Variables

Data will be summarized with respect to safety observations. Monitoring of AEs, physical examinations, vital signs, ECGs, safety and tolerability monitoring evaluations, clinical laboratory evaluations, and special procedures are detailed in [Section 6.3](#).

All available safety data for all randomized subjects who receive at least one dose of PRA023 will be included in the safety analysis, which will be primarily descriptive.

The safety variables will be:

- Hematology, chemistry, coagulation, and urinalysis
- Vital signs
- ECG parameters

- Physical examination
- AEs and SAEs
  - AEs of special interest: infections, acute infusion reaction (within 1 hour of completion of infusion), and peri-infusion reaction (within 24 hours of completion of infusion)
  - AEs in subjects who are ADA positive

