## 9 STATISTICAL METHODOLOGY

This section describes the statistical analysis as it is foreseen at the time of planning the trial. Statistical methods will be further detailed in the SAP. The SAP will provide details about methods of analysis and the specific planned analyses, and will be prepared and approved by Prometheus Biosciences and its designees before study database lock.

Any deviations from the analysis plan, and the reasons for such deviations, and all alternative or additional statistical analyses that may be performed will be justified in the clinical study report.

All individual data as well as results of statistical analyses will be presented in individual subject data listings and statistical summary tables. In general, continuous variables will be summarized using the following standard descriptive summary statistics: number of observations, arithmetic mean, standard deviation (SD), coefficient of variation (CV), minimum, median and maximum. The geometric mean (GM) will be reported for PK and PD variables where appropriate. Categorical data will be summarized as number and percentage of subjects. Shift tables will be provided, where appropriate.

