#### **9.3.7.2 Medical History, Chest X-ray, ECGs and Physical Examination**

Medical history, chest x-ray, ECGs and physical examination data will be listed by subject. All medical history will be coded using the most current version of MedDRA. Changes in ECGs and physical examination will be described in the text of the final study report.

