### **9.3.7.3 Clinical Laboratory and Vital Signs**

All clinical laboratory results and vital signs measurements, and their change from baseline, will be summarized by treatment and time point of collection.

A shift table describing out-of-normal range shifts will be provided for clinical laboratory results.

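### The protocol plans only a listing and a narrative for ECGs, so the placebo-controlled ECG intervals get no by-arm summary

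*Protocol*

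**What the plan says.** The ECG-specific analysis text appears twice. In the protocol synopsis (Statistical Methods, Adverse Events), ECGs are listed by subject along with medical history, chest x-ray and physical examination, and then: "Changes in ECGs and physical examinations will be described in the text of the final report". Section 9.3.7.2 says the same: "Medical history, chest x-ray, ECGs and physical examination data will be listed by subject", followed by "Changes in ECGs and physical examination will be described in the text of the final study report".

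Section 9.3.7.3 treats the other objective safety measurements differently: "All clinical laboratory results and vital signs measurements, and their change from baseline, will be summarized by treatment and time point of collection".

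Two more general statements also bear on ECGs. Section 8.3 opens with "Data will be summarized with respect to safety observations", and its list of safety variables includes "ECG parameters". Section 9 says "In general, continuous variables will be summarized using the following standard descriptive summary statistics". Neither describes an ECG table.

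Section 6.3.4 names heart rate, PR, QRS and QT as the parameters to be assessed. It asks for a manual over-read when the automatic QT or QTc is above 480 msec, "or if either has increased by 50 msec or more over the baseline value". It names no rate-correction formula. A separate paragraph requires any indication of QT prolongation or Torsade de Pointes during treatment to be recorded as an adverse event.

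**The concern.** Safety and tolerability over the 12-week induction is a primary objective. Every subject in the open-label extension receives PRA023 (Section 4.1), so the Induction Period is the only time when ECGs on drug can be set against ECGs on placebo. A listing with a narrative can bring out individual abnormal tracings. It cannot show whether mean PR, QRS or QTc moved differently in the two arms, or how many subjects per arm had a large change. That comparison is protected by randomisation and blinding, and its data are already being collected, but the protocol text does not ask for it.

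There is a second, smaller issue. If a by-arm count is built on the Section 6.3.4 limits, those limits mix QT with QTc and leave the correction unnamed. The count would then depend partly on heart rate, and partly on whichever formula the ECG machine applies.

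**Working it through.** The plan states no figure on this point, so the check is a comparison of sections with some illustrative arithmetic.

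**1. Specific text against general text.**

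| Data | Specific analysis text | By treatment and time point? |
|---|---|---|
| Laboratory results | Section 9.3.7.3 | Yes, with change from baseline |
| Vital signs, including heart rate (Section 6.3.2) | Section 9.3.7.3 | Yes, with change from baseline |
| Adverse events, including QT prolongation recorded as one | Section 9.3.7.1 | By treatment |
| ECG PR, QRS, QT, QTc | Synopsis and Section 9.3.7.2 | No: listing and narrative |

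The statements in Sections 8.3 and 9 are general and name no ECG table. The only text specific to ECGs says listing and description. At best the protocol is inconsistent with itself.

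**2. The data exist.** Table 1 schedules an ECG at screening. Table 2 schedules ECGs at Week 0, Week 12 and early termination, in both arms.

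**3. What a by-arm table would deliver.** The inputs are 60 per arm (Section 8.2, Cohort 1) and an assumed SD of 15 to 20 msec for change in QTc. The documents give no SD. The 95% half-width is 1.96 × SD × √(2/n):

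- n = 60, SD 15: 1.96 × 15 × √(2/60) = 5.4 msec
- n = 60, SD 20: 1.96 × 20 × √(2/60) = 7.2 msec

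If both cohorts are pooled at the protocol's upper figure of about 170 (85 per arm), the range is 1.96 × 15 × √(2/85) = 4.5 msec to 1.96 × 20 × √(2/85) = 6.0 msec. Missing Week 12 ECGs would widen these a little.

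**4. Why a by-arm count should use QTc.** Hold QTc fixed and let only heart rate (HR) change. Under Fridericia, QT = QTc × (60/HR)^(1/3). With QTc assumed at 400 msec:

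- HR 90 to 60: 349 to 400, a rise of 51 msec
- HR 85 to 70: 356 to 380, a rise of 24 msec
- HR 80 to 70: 363 to 380, a rise of 17 msec

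So uncorrected QT can cross the 50 msec limit with no change in QTc, but of these three cases only the 30 bpm fall does so. The 480 msec limit is harder to reach: at an assumed QTc of 450 msec, QT exceeds 480 only at about 49 to 52 bpm or below, depending on the formula.

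**5. Why the formula should be named.** At a constant QTc of 420 msec, a fall from 80 to 60 bpm raises QT by 38 msec under Fridericia, 56 under Bazett and 38 under Framingham. How much of a QT rise is attributed to heart rate, and so whether a subject counts as crossing 50 msec on QTc, depends on the formula. The heart rates and QTc values in steps 4 and 5 are assumptions; the documents report none.

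**The case against.** The case for leaving the text alone has real weight.

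- **Main SAP V01 is not among the documents.** The protocol defers detailed methods to the SAP, and the addendum covers only multiplicity and the CDx analyses. V01 may already contain by-treatment ECG tables. This stands, and it limits the point to the protocol text.
- **Saying that ECGs are listed does not say that they are only listed.** Sections 8.3 and 9 promise summaries in general terms. This stands in part. Those sentences permit an ECG table but do not specify one, and the specific text points the other way.
- **The prior concern is low.** The protocol reports no ECG or functional cardiovascular findings in monkeys over 6 months and no clinically significant ECGs in Phase 1. QT is not an adverse event of special interest. The primary safety endpoint is adverse events and markedly abnormal laboratory values, not ECG intervals. This stands, and it is why the point is a cheap improvement and not a major defect.
- **Section 9.3.7 rules out formal statistical evaluation of safety.** A descriptive by-arm table is not a test. Laboratory results and vital signs get one under the same rule.

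A reader might also infer three stronger things that the documents do not support.

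- *That the arms are not compared on ECG findings at all.* QT prolongation recorded as an adverse event is tabulated by treatment, and heart rate is summarised by arm as a vital sign.
- *That Section 6.3.4 is a counting rule on uncorrected QT.* It covers QT or QTc, and it triggers an over-read with further work-up if the prolongation is verified. Nothing says that crossing a limit on QT alone automatically becomes an adverse event.
- *That adverse event rates will be biased against the arm that improves more, because heart rate falls as colitis settles.* The mechanism is possible, but it needs a large individual fall in resting heart rate, and the documents give no heart-rate data by arm or by response.

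**Conclusion.** The point holds for the protocol text. The ECG-specific analysis is a listing and a narrative, and the only placebo-controlled ECG interval data have no planned by-arm summary, while laboratory results and vital signs do. What is forgone is an estimate of the Week 12 difference in QTc change with a half-width of about 5.4 to 7.2 msec in Cohort 1 (assumed SD 15 to 20 msec, 60 per arm), together with per-arm counts of large changes.

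Because the Section 6.3.4 trigger accepts uncorrected QT and names no correction, any such count should rest on QTc under one stated formula. Bias against the effective arm remains a possibility only and is not part of the conclusion. The conclusion assumes that SAP V01 does not already supply the tables. This is a cheap improvement.

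**What to change.** In the synopsis and Section 9.3.7.2, keep the by-subject listing and add the following:

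- For the Induction Period, heart rate, PR, QRS and QTc (one named correction, for example Fridericia), with change from baseline, are summarised descriptively by treatment and visit.
- Optionally, the Week 12 PRA023-minus-placebo difference in change is given with a 95% CI, as an estimate without a test.
- The number and percentage of subjects per arm exceeding the limits already in Section 6.3.4 (above 480 msec; increase of 50 msec or more) are counted on QTc. Uncorrected QT is listed only.

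Leave the Section 6.3.4 over-read trigger as it is. This change concerns reporting, not clinical handling. If SAP V01 already specifies these tables, align the protocol wording with it and add nothing else.

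The cost is one or two standard tables from data already collected, with no new procedure or visit.

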# 1 BACKGROUND AND RATIONALE

## 1.1 Background

PRA023 is a humanized monoclonal antibody that binds human tumor necrosis factor-like cytokine 1A (TL1A) with high affinity and specificity. TL1A is a cytokine which is part of the tumor necrosis factor (TNF) superfamily protein and is secreted by both innate and adaptive immune cells as well as by endothelial cells.

TL1A binds to death receptor 3 (DR3) that is found primarily on T cells, natural killer (NK) and NK-T cells, innate lymphoid cells (ILC) and epithelial cells (Valatas 2019) and potently drives Th1, Th2, Th9 and Th17 responses. In addition, it is induced in antigen-presenting cells by toll like receptor (TLR) ligands and FcR (Fc receptor) cross-linking and in T cells by T-cell receptor (TCR) stimulation (Prehn 2007). TL1A occurs as both membrane-bound and soluble forms (Ferdinand 2018).

TL1A has been shown to be upregulated in mucosa and serum of patients with inflammatory bowel disease (IBD) (Bamias 2003, Bamias 2010). TL1A and DR3 are abundantly localized at inflamed intestinal areas of patients with IBD and mice with experimental ileitis or colitis and actively participate in the immunological pathways that underlie mucosal homeostasis and intestinal inflammation (Valatas 2019). Furthermore, TL1A polymorphisms have been shown to be associated with susceptibility to IBD (Yamazaki 2005, Yang 2008) and with disease severity (Cleynen 2013, Richard 2015).

In dextran sodium sulfate (DSS) and adoptive transfer mouse models, antibodies against TL1A led to reduced inflammation and reversal of fibrosis, even when treatment was administered late in the course of disease, after inflammation and fibrosis has been established (Shih 2014).

Prometheus Biosciences has developed PRA023, a humanized IgG1 kappa (IgG1 $\kappa$ ) monoclonal antibody that binds to both membrane-bound and soluble forms of TL1A with high affinity and specificity and blocks the binding of TL1A to its functional receptor DR3. Prometheus Biosciences is also developing a genetic-based companion diagnostic (CDx) to identify patients who are predisposed for increased expression of TL1A and therefore potentially more likely to respond to PRA023. By targeting both intestinal inflammation and fibrosis, PRA023 has the potential to substantially improve outcomes for moderate to severe IBD patients with increased TL1A expression.

PF-06480605 is an anti-TL1A monoclonal antibody developed by Pfizer and studied in healthy volunteers and patients with ulcerative colitis (UC) (Banfield 2020, Danese 2020). Target engagement was demonstrated in healthy volunteers as confirmed by dose-dependent increases in mean total soluble tumor necrosis factor-like cytokine 1A (sTL1A). In a Phase 2a open-label study with centrally read endoscopy in subjects with moderately to severely active UC, treatment with the anti-TL1A antibody led to significant endoscopic improvement (38%), clinical remission (24%), histologic improvement, and decrease in biomarkers (fecal calprotectin and hsCRP) at Week 14. PF-06480605 appeared to have an acceptable safety and tolerability profile.

Prometheus Biosciences is undertaking a Precision Medicine approach to the development of an anti-TL1A therapeutic for treatment of moderate to severe Crohn's Disease (CD) and UC, using a

CDx to identify patients most likely to respond to study drug. The advantage of this unique, precision-based approach in IBD is the ability to identify patients more likely to respond to our therapeutics in targeted clinical trials, with the ultimate goal of bringing therapeutic drugs to patients with significantly better clinical efficacy.

This is a Phase 2, multi-center, double-blind, randomized, placebo-controlled proof of concept study designed to assess the safety, tolerability, and efficacy of PRA023 following 12 weeks of induction therapy in subjects with moderately to severely active UC.

## 1.2 Study Rationale

IBD is a complex disease with many contributing factors including environmental influences, genetics, and immunologic factors. UC and CD are two of the most common forms of IBD. Both UC and CD are chronic, relapsing, remitting, inflammatory conditions of the gastrointestinal (GI) tract that begin most commonly during adolescence and young adulthood. UC involves the mucosal layer of the large intestine, and symptoms include abdominal pain and diarrhea, frequently with blood and mucus. CD can affect the entire thickness of the bowel wall and all parts of the GI tract from mouth to anus. CD symptoms include abdominal pain, diarrhea, and other more insidious symptoms such as weight loss, nutritional deficiencies, and fever. The prevalence of IBD globally is approximately 5 million and affects over 2 million people in the US ([Ananthkrishnan 2020](#)). A hallmark of IBD is the cytokine responses that govern the initiation, evolution, and ultimately, the resolution of these forms of inflammation. Many immune cells, cytokines, and chemokines of the adaptive and innate immune systems play a role in IBD, including but not limited to IL-12, IL-23, IFN $\gamma$ , IL-17, IL-22, and TL1A ([Roberts-Thomson 2011](#), [Strober 2011](#)).

The current standard of care for the treatment of patients with moderate to severe IBD are generally immunomodulatory agents that are anti-inflammatory. None of the therapies address fibrosis in IBD. While intestinal fibrosis is a well-recognized complication of CD, clinical colonic strictures has been reported in up to 11% of patients with UC ([De Dombal 1966](#), [Gumaste 1992](#)). In a study that examined 89 consecutive UC colectomy specimen from Cleveland Clinic, submucosal fibrosis was detected in 100% of the specimen ([Gordon 2018](#)). The degree of fibrosis was associated with the severity of chronic mucosal injury but not acute inflammation. Subclinical fibrosis in the colonic wall may have significant clinical implications such as abnormalities leading to symptoms such as diarrhea, abdominal pain, urgency, and incontinence ([Bassotti 2006](#)). It has long been speculated that intestinal fibrosis may be the underlying cause of persistent UC symptoms, after the resolution of inflammation, that is commonly misclassified as irritable bowel syndrome ([Hirten 2017](#)). To date, no approved therapies for IBD address or treat the intestinal fibrosis.

Furthermore, since the approval of the first anti-TNF agent for the treatment of CD in 1998, the availability of newer biological agents, including anti-integrin (vedolizumab), Janus kinase (JAK) inhibitors (tofacitinib), and anti-IL12/23 (ustekinumab) has improved the care of moderate to severe UC. However, none of these subsequently approved therapies have demonstrated significant improvement in effect size relative to anti-TNF. Moreover, among those patients who do respond, up to 45% will lose response over time ([Roda 2016](#)). Current therapies used in the

treatment of UC apply a one-size-fits-all approach without regard to genetic or biologic variations in the patient. Existing approaches continue to leave unmet patient need.

Given established clinical validation of the target with PF-06480605, the current placebo-controlled Phase 2 induction study is designed to demonstrate the efficacy of PRA023 in subjects with moderately to severely active UC. In addition, this induction study is designed to assess the effectiveness of the genetic CDx for the purpose of selection of subjects whose disease is driven by the TL1A pathway and therefore, have a higher response rate to treatment with an anti-TL1A antibody. The study is also designed with an open-label extension study to ensure that subjects who benefit from the therapy have the option to continue therapy.

In parallel to this study, an open-label CD study (PRA200-103) will be conducted to demonstrate the proof of concept of PRA023 for induction therapy in subjects with moderately to severely active CD.

### 1.3 PRA023 Mechanism of Action and Nonclinical Data

The Investigator's Brochure should be referenced for a complete summary of data and information collected about PRA023 (including the principal data and findings from the nonclinical pharmacology, pharmacokinetic, and toxicological studies conducted to date).

#### 1.3.1 Pharmacology

PRA023 is a humanized IgG1 $\kappa$  antibody that binds human TL1A with high affinity and specificity and neutralizes TL1A functional activity in vitro and ex vivo cell-based assays. PRA023 binds to both human and cynomolgus TL1A with a similar sub-nanomolar EC50 (half maximal effective concentration) and with similarly high affinity (KD [dissociation constant] values of [REDACTED] nM and [REDACTED] nM, respectively). In addition, PRA023 is specific for TL1A and does not bind to other TNF super family members. Together, these data show that PRA023 is a high affinity humanized monoclonal antibody with selectivity for human and cynomolgus TL1A.

PRA023 has the capacity to block human TL1A-induced caspase activation and apoptosis in the TF-1 functional assay with an IC50 (half maximal inhibitory concentration) of [REDACTED] nM. Similarly, PRA023 blocked monkey TL1A-induced caspase activation with an IC50 of [REDACTED] nM. In a monkey whole blood assay, PRA023 inhibited the immune complex/TL1A enhancement of IFN- $\gamma$  release with an IC50 of [REDACTED] nM and IC90 (90% maximal inhibitory concentration) of [REDACTED] nM.

A single dose pharmacokinetic/pharmacodynamic (PK/PD) study in cynomolgus monkeys demonstrated a dose-dependent pharmacologic effect of PRA023 on the inhibition of TL1A-mediated IFN- $\gamma$  release from peripheral blood mononuclear cells (PBMCs) in whole blood at doses of  $\geq$  [REDACTED] mg/kg. The observation that greater concentrations (approximately [REDACTED] fold) of serum PRA023 were required to elicit this effect in animals treated with PRA023 versus when PRA023 was added in vitro to monkey whole blood indicates that a higher concentration of drug is required for biologic effect in vivo. In addition, a dose-dependent increase in circulating

sTL1A concentrations was observed at all dose levels. This suggests that systemic sTL1A concentrations may be a useful PD marker for target engagement by PRA023.

